6. ENDPOINTS AND COVARIATES

6.1. Safety Endpoints

- Adverse drug reactions: Adverse events determined to be related to V fend by the physician
- Adverse events: All-causality adverse events
- Serious adverse events or adverse drug reactions: Adverse events or adverse drug reactions determined to be serious by the physician
- Safety specifications
 - Hepatic toxicity
 - QT prolongation, ventricular tachycardia, ventricular fibrillation, arrhythmia, atrioventricular block complete
 - Visual events
 - Phototoxicity
 - Peripheral neuropathy such as Guillain-Barre syndrome
 - Renal failure
 - Hematologic disorder
 - Interstitial pneumonia
 - Hart failure
 - Consciousnessdistubed
- Major investigation items: Events to be handled as major investigation items among safety specifications are listed below.
 - Hepatic toxicity
 - Visual events
- Laboratory test

White blood cell count, neutrophil count, platelet count, total bilirubin, AST (GOT), ALT (GPT), Al-P, GGT, CRP, BUN, and serum creatinine before the start of treatment with Vfend and by the end date of the observation period in this study

6.2. Effectiveness Endpoints

• Presence or absence of invasive fungal infections: The onset of invasive fungal infections during the observation period will be judged. If the treatment with this product is continued at the completion of

study period, the onset of invasive fungal infections until the completion of study period will be judged.

- Without onset
- With onset
- Indeterminate
- In case of "with onset" of invasive fungal infections, it will be classified as follows according to the diagnostic criteria of the European Organization for Research and Treatment of Cancer/Mycoses Study Group (EORTC/MSG).
 - Proven diagnosis*
 - Probable diagnosis^{**}
 - Possible case***

*: Proven diagnosis: Patients who have clinical symptoms and findings of inflammation caused by mycosis and the causative fungi are proved from the histological diagnosis of the focus of infection or mycological diagnosis from the sterile site, etc.

: Probable diagnosis: At least one host factor + one clinical criterion + one mycological criterion *: Possible case: At least one host factor + meeting one clinical criterion but no mycological criterion

6.3. Other Endpoints

Not applicable

6.4. Covariates

As for the safety and effectiveness of Vfend, there are no covariates identified from clinical study data thus far obtained.

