# 7.5. Study size

#### 7.5.1. Planned sample size

200 patients (100 patients each for children and adults)

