Although the incidence of visual events varies among different studies (study A1501073: 12.0%, study A1501038: 4.4%, and study A1501096: 42.9%), if it is presumed that there is the incidence of 5% or higher, the expected value of the incidence to be observed in 200 patients will be at least 10 patients. While it is possible that there may be no patient who discontinues the administration of this product due to visual events based on the results of clinical studies, if any patient who discontinues the administration of this product is observed, how it happened will be examined.

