2.2. Study Objectives

This surveillance is intended to grasp the following items, etc. for the safety and effectiveness of this product in daily clinical practice for prophylactic administration of this product for invasive fungal infections in pediatric and adults and review the necessity for further special investigation and post-marketing clinical study.

- Unknown adverse reactions including the time of long-term use
- Occurrence of adverse reactions under actual clinical settings
- Factors considered to affect the safety and effectiveness of this product

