4. HYPOTHESIS AND DECISION RULES

4.1. Statistical Hypothesis

Because this study is not a confirmatory investigation, the tests are considered as exploratory tests. The P value of test results will be evaluated as descriptive statistics. The significance level is not provided, but a threshold may be set afterwards for the purpose of screening.

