8.1.3. Analysis of Binary Data

The frequency and proportion will be calculated. If the confidence interval of proportion is calculated, two-sided 95% confidence interval (exact method) will be calculated.

If the proportion is compared between subgroups, risk ratio and its 95% confidence interval, and risk difference and its 95% confidence interval will be calculated. In addition, risk ratio and its 95% confidence interval will be graphically presented (see Appendix 2). If the number of patients in at least one category compared is \leq 5, the number of patients and proportion will be calculated but risk ratio and its 95% confidence interval, and risk difference and its 95% confidence interval will not be calculated.

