8.2.3.4. Subgroup Analysis

The number and proportion of patients who experienced at least one adverse drug reaction will be tabulated for each factor specified in Section 5.4. To evaluate the relationship between patient background factors and the development of adverse drug reactions, the analysis specified in Section 8.1.3 will be performed. Risk ratio and risk difference will not be calculated for concomitant use of steroids or immunosuppressants other than steroids.

The listing of adverse drug reactions will be prepared for contraindicated patients. The number and proportion of patients with adverse drug reactions will be tabulated by SOC and PT as necessary.

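### The background-factor risk ratios are crude and pooled over children and adults, so a factor that tracks age can be confounded by age; add an age-stratified estimate and restrict the elderly comparison to patients aged 15 or over.

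*SAP*

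**What the plan says.** One of the three objectives in SAP 2.2 is to identify "Factors considered to affect the safety and effectiveness of this product". SAP 6.4 says that "there are no covariates identified from clinical study data thus far obtained".

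The comparison method is in SAP 8.1.3: "If the proportion is compared between subgroups, risk ratio and its 95% confidence interval", together with the risk difference and its interval, and nothing is calculated when a compared category has five patients or fewer. For safety, SAP 8.2.3.4 applies this to the proportion with at least one adverse drug reaction: "To evaluate the relationship between patient background factors and the development of adverse drug reactions, the analysis specified in Section 8.1.3 will be performed". SAP 8.2.4.4 does the same for the infection rate and the success rate. The factors are those listed in 5.4, taken over the whole analysis set; no stratified or multivariable analysis appears anywhere. Factors with a risk ratio of at least 2 or at most 0.5 go on to further tables (8.2.3.5) or listings (8.2.4.5).

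Protocol 7.5.1 plans 200 patients, half children and half adults. Age enters the SAP as a factor in its own right: Age (1) splits at 15 years, Age (2) compares 65 and over with under 65, and several tables are given by age. None of these adjusts another factor's ratio for age.

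**The concern.** A pooled crude ratio mixes the effect of a factor with the effect of age when two conditions hold together: the factor is more common in one age group, and the outcome is too. Type of transplant, indication, concomitant drugs and organ dysfunction could all plausibly differ between children and adults, although the documents do not say by how much.

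The documents' own figures suggest that at least one outcome may differ. Visual events are put at 42.9% in the Japanese paediatric study, against 12.0% and 4.4% in the two foreign transplant studies (Protocol 7.5.2). Hepatic toxicity, by contrast, is judged similar in adults and children.

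At stake is the factor-finding objective. A ratio that reflects age could be read as the effect of a drug or a disease feature. Age (2) has a sharper version of the problem: no child is 65 or over, so the elderly are compared with a reference made up of younger adults and every child.

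**Working it through.** **The plan's own figures.** The sample-size statements reproduce. The exact binomial probability of at least 31 cases among 200 at 20% is 0.957 (stated: about 95%). Wald intervals at 50% are 40.2 to 59.8% for n = 100 and 43.1 to 56.9% for n = 200 (stated: 40-60% and 43-57%). The plan gives no figure for confounding, so the rest is derived.

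**Inputs from the documents.** 100 children and 100 adults. Hepatic toxicity 19.0% (Japanese children) and 20.2% (study A1501073). Visual events 42.9% (Japanese children) and 12.0% (A1501073).

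**Assumptions.** The foreign transplant studies represent adults. Any adverse drug reaction is approximated by hepatic or visual events, taken as independent. Factor prevalence by age is unknown and shown as a range.

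**Any-reaction proxy.**
- Children: 1 − (1 − 0.190)(1 − 0.429) = 0.537
- Adults: 1 − (1 − 0.202)(1 − 0.120) = 0.298

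**Expected crude ratio for a factor with no effect.** With prevalence q in children and 1 − q in adults, and equal group sizes:

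RR = [q·pC + (1 − q)·pA] / [(1 − q)·pC + q·pA]

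At 80/20: (0.8 × 0.537 + 0.2 × 0.298) / (0.2 × 0.537 + 0.8 × 0.298) = 0.489 / 0.346 = 1.41.

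The last two columns are for the proxy and come from simulation.

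| Prevalence, children/adults | Proxy, 53.7% v 29.8% | 40% v 30% | Hepatic, 19.0% v 20.2% | Crude CI excludes 1 | Crude RR ≥2 or ≤0.5 |
|---|---|---|---|---|---|
| 60/40 | 1.12 | 1.06 | 0.99 | about 10% | 0.1% |
| 70/30 | 1.26 | 1.12 | 0.98 | about 27% | 0.5% |
| 80/20 | 1.41 | 1.19 | 0.96 | about 54% | 3% |
| 90/10 | 1.59 | 1.26 | 0.95 | about 79% | about 12% |

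The true ratio is 1 in every row. In the same proxy datasets, the Mantel-Haenszel ratio stratified at 15 years has a median of 1.00, and its interval excludes 1 in about 5%.

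**Ceiling.** A factor with no effect cannot have an expected crude ratio above the age ratio itself, here 0.537/0.298 = 1.80. Age alone therefore does not bring the expected proxy ratio to 2.

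**Age (2).** Suppose the targets are met, k adults are 65 or over, and adult risk does not depend on age. The under-65 reference then has 100 children and 100 − k adults.
- k = 10: children are 100/190 = 53% of the reference; its risk is (53.7 + 90 × 0.298)/190 = 0.424; RR = 0.298/0.424 = 0.70.
- k = 40: children are 100/160 = 63%; risk (53.7 + 60 × 0.298)/160 = 0.447; RR = 0.298/0.447 = 0.67.

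By simulation, the ratio is 0.5 or less in about 34% of datasets at k = 10 and 16% at k = 40. Restricted to patients aged 15 or over, these fall to about 16% and 3%; what remains is chance.

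**The case against.** The strongest reply is that this is a descriptive screen. SAP 4.1 says: "Because this study is not a confirmatory investigation, the tests are considered as exploratory tests". P values are descriptive, and passing the screen leads only to another table or listing. Protocol 7.9 concedes that confounding may not be fully handled. Results by age are planned for adverse drug reactions, the major investigation items, and the infection and success rates.

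This supports a low severity but does not remove the point. An exploratory label does not make a biased ratio informative. Protocol 7.9 attributes the limitation to background data that may be missing, whereas age is recorded at registration. The tables by age do not show whether another factor's ratio survives within age groups.

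Several objections to the size do stand:

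- A reader might apply the visual-event rates and find that a factor with no effect, at 80/20, has a crude ratio of (0.8 × 0.429 + 0.2 × 0.120)/(0.2 × 0.429 + 0.8 × 0.120) = 2.02, which would pass the screen. The SAP plans no visual-event ratio by factor: 8.2.3.4 uses at least one adverse drug reaction, and the version 3.0 change log records that subgroup analyses of the major investigation items were deleted.
- The age contrast is weak evidence. The 42.9% rests on 21 children, and the comparison also mixes study and region. The documents do not state the ages in the two foreign studies.
- A reader might infer that the even split causes the confounding. It does not, though it makes any confounding larger: at 80/20 the proxy ratio is about 1.13 with 10 children among 200, against about 1.4 with 100.
- For effectiveness, the documents give no rate by age, so bias there is possible but cannot be sized.

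**Conclusion.** The point holds in a limited form. The risk ratios and risk differences are crude, pooled over a planned even mix of children and adults, and never adjusted for age. They can be confounded for any factor tied to age where the outcome also differs by age. The documents do not support saying that they are confounded in general.

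Under the any-reaction proxy, the expected ratio for a factor with no effect runs from 1.12 to 1.59. It is smaller with a narrower age gap and negligible at the hepatic toxicity rates. The practical risk is a confidence interval that wrongly excludes 1. Crossing the 2 or 0.5 screen is uncommon up to 80/20 and reaches about 12% only at 90/10. These figures rest on assumed prevalences, on independence of hepatic and visual events, and on treating the foreign studies as adult.

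Age (2) is the clearest case. It needs no prevalence assumption, only a difference in outcome between children and adults; under the proxy, the elderly would appear to have about 0.7 times the risk with no elderly effect at all.

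This is a cheap improvement to an exploratory analysis, not a flaw that undermines the study.

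**What to change.** - In SAP 8.1.3, 8.2.3.4 and 8.2.4.4, keep the crude ratios. For each factor other than age, add the counts by Age (1) (under 15; 15 or over) and the Mantel-Haenszel risk ratio and risk difference stratified by Age (1).
- In 8.2.3.5 and 8.2.4.5, apply the screen (at least 2 or at most 0.5) to the stratified ratio.
- Restrict the Age (2) comparison to patients aged 15 or over.
- In 6.4, name Age (1) as the stratification variable.
- State in 8.1.3 how the rule on five or fewer patients applies once the data are stratified.

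**Cost.** SAP wording and one extra program, using data already collected. Intervals widen when a factor is strongly tied to age: under the proxy, the standard error of the log ratio is about 5% larger at 70/30, 18% at 80/20 and 57% at 90/10. A stratum with no events adds no information, which will matter if infections are rare.

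The stratified screen is also noisier where age does not matter. With a 30% risk in both groups and 90/10 prevalence, it fires by chance in about 7% of datasets, against 0.3% for the crude ratio. The interval should therefore be read beside the screen. Stratifying at 15 years leaves any confounding by age within each group.

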7. HANDLING OF MISSING DATA

When the seriousness of adverse events, change in treatment with Vfend, and outcome of adverse events are missing, these data are handled as "unknown" for counting. Because information on causal relationship will be collected by dosage form in this study, causal relationship will be handled as "missing" only when it is missing for all of injection, tablet, and dry syrup and will be handled as "related" for counting. If data on effectiveness endpoints are missing, they will be handled as "missing."

The strategy for handling data with uncompleted cleaning is described below.

- Items of missing data: The items will be handled as missing (category of categorical variable is "unknown") for both tabulation and listing.
- Items of inconsistent data: The items will be handled as missing for both tabulation and listing. However, the list of data handling will be separately prepared.

• No signature: Descriptions in the case report form without the signature of the contracted physician (including the case report form with the signature of an uncontracted physician only) will be handled as missing for both tabulation and listing. If there is a field for the date of signature but there is no date of signature or if there is inconsistency in the date entered (e.g. before the day of initiation of treatment, future date), descriptions in the case report form will be regarded as not signed.

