# [ DOSAGE AND ADMINISTRATION ]

<for Intravenous Use>

Adult	Voriconazole is administered by intravenous drip infusion at the dose of 6 mg/kg twice daily on day 1 and 3 mg/kg or 4 mg/kg twice daily from day 2 onward.
Children (Aged 2 to <12 and 12 ≥ whose body weight is less than 50 kg)	9 mg/kg as voriconazole twice daily on day 1 and 8 mg/kg twice daily from day 2 should be given intravenously. Dose may be increased depending on condition of patients or if poorly responded_by 1 mg/kg at a time, and dose in intolerant patients should be reduced by 1 mg/kg at a time.
Children (Aged ≥12 whose body	6 mg/kg as voriconazole twice daily on day 1 and 4 mg/kg twice
weight is 50 kg or more)	daily from day 2 should be given intravenously.

<tablet></tablet>	
Adult (body weight ≥40 kg)	A recommended oral dose of voriconazole is 300 mg twice daily between meals on day 1, and 150 or 200 mg/dose twice daily between meals on day 2 and thereafter. Dose may be increased depending on condition of the patients or if poorly responded; provided that a total daily dosage should not exceed 400 mg/dose twice daily on day 1 and 300 mg/dose twice daily on day 2 and thereafter.
Adult (body weight <40 kg)	A recommended oral dose of voriconazole is 150 mg twice daily between meals on day 1, and 100 mg/dose twice daily between meals on day 2 and thereafter. Dose may be increased from day 2 onward depending on condition of patients or if poorly responded; provided that a total daily dosage should not exceed 150 mg/dose twice daily.
Children (Aged 2 to <12 and ≥12 whose body weight is less than 50 kg)	After the administration of Voriconazole injection, a recommended maintenance oral dose of voriconazole following injection therapy is 9 mg/kg/dose twice daily between meals. Dose may be increased by 1 mg/kg at a time depending on condition of patients or if poorly responded, and dose in intolerant patients should be reduced by 1 mg/kg at a time (unless the dosage was at its maximum 350 mg, in which case, dose should be reduced by 50 mg at a time). A total daily dosage should not exceed 350 mg/dose twice daily.
Children (Aged ≥12 whose body weight is 50 kg or more)	After the administration of Voriconazole injection, a recommended maintenance oral dose of voriconazole following injection therapy is 200 mg/dose twice daily between meals; which may be increased up to 300 mg/dose twice daily depending on condition of patients or if poorly responded.
<dry syrup=""></dry>	

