#### 7.3.7. Adverse events

Confirm the status of adverse events from the initiation of administration of this product to the completion of observation period, and record the following information. Upon discovery of an adverse event, the attending doctor should take appropriate actions, and promptly report to Pfizer Japan Inc. (hereinafter "Sponsor"), and if causal relation with this product cannot be ruled out, the doctor should follow up the event until the adverse event or its sequelae are resolved or stabilized at the level acceptable by the attending doctor and Sponsor.

Moreover, a study should be conducted on patients in whom a serious adverse reaction, or an adverse reaction not specified in the package insert occurred if it is determined necessary by Sponsor.

- (1) Presence/absence of adverse event
- (2) Name of adverse event
- (3) Date of occurrence
- (4) Action
- (5) Seriousness
- (6) Outcome
- (7) Causality

[If the adverse event is associated with abnormal change in laboratory values, i.e., laboratory tests, the following information should also be recorded.]

- (1) Laboratory parameter
- (2) Site reference value
- (3) Unit
- (4) Date of test
- (5) Results

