# 9.3. Causality assessment

The investigator is required to assess and record the causal relationship. For all AEs, sufficient information should be obtained by the investigator to determine the causality of each adverse event. For AEs with a causal

relationship to this product, follow-up by the investigator is required until the event and/or its sequelae resolve or stabilize at a level acceptable to the investigator, and Pfizer concurs with that assessment.

An investigator's causality assessment is the determination of whether there exists a reasonable possibility that this product caused or contributed to an adverse event. If the investigator's final determination of causality is "unknown" and s/he cannot determine whether this product caused the event, the safety event must be reported within 24 hours.

If the investigator cannot determine the etiology of the event but s/he determines that this product did not cause the event, this should be clearly documented on the case report form and the NIS AEM Report Form.

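### The causality rule in SAP 7 counts a wholly blank assessment as a reaction but not a blank for the form in use when another form is marked not related, and SAP 6.1 read literally omits 'unknown'

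*SAP*

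**What the plan says.** SAP 7 (Handling of Missing Data) states that "information on causal relationship will be collected by dosage form in this study". Causality is treated as missing "only when it is missing for all of injection, tablet, and dry syrup", and the event is then counted as related. The section does not refer to the form the patient was taking, and it does not say how partly blank, discordant or 'unknown' answers are combined.

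The same section ends with rules for data whose cleaning is not complete. The first reads "Items of missing data: The items will be handled as missing", and a categorical item then goes into an 'unknown' category. No exception is stated for causality.

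SAP 6.1 defines the endpoint: "Adverse drug reactions: Adverse events determined to be related to V fend by the physician".

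Protocol 9.3 allows a final causality determination of 'unknown'. For an investigator in that position it says that if "s/he cannot determine whether this product caused the event, the safety event must be reported within 24 hours". Protocol 7.3.7 uses a different threshold for follow-up: "if causal relation with this product cannot be ruled out, the doctor should follow up the event".

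Protocol 7.3.2 records dosage form and administration period for each patient. The dosing text in Protocol 7.2.1 introduces the children's oral regimens with "After the administration of Voriconazole injection, a recommended maintenance oral dose of voriconazole following injection therapy".

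**The concern.** The SAP's one imputation rule for causality is conservative: if the physician has entered nothing, the event counts as a reaction. The trigger, however, is whether all three fields are empty, not whether the forms the patient actually received were assessed. Take a patient who moves from injection to tablets and has an event on tablets. If injection is marked not related and the tablet field is empty, there is no judgement on the form in use, yet the rule does not apply. The event has no 'related' entry and so drops out of the SAP 6.1 count. A physician who writes 'unknown' has likewise not excluded a relationship, but that event fails the literal definition while a blank sheet meets it.

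The reaction definition feeds the reaction tables in SAP 8.2.3.1 (by age, hepatic and renal dysfunction, long-term treatment, change in treatment and outcome), the time to onset of the major investigation items, the subgroup risk ratios in 8.2.3.4 and the exploratory tables in 8.2.3.5. The all-causality tables in 8.2.3.2 are split only by SOC, PT and seriousness. A reaction lost in one age group would therefore not show in any planned all-causality table by age. The conflict with the cleaning rule adds a practical risk: two programmers could derive different reaction counts from the same data.

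**Working it through.** **Step 1. The rule, case by case.** The documents state no figure for this rule, so the check is to run the possible answers through SAP 7 and then SAP 6.1.

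| Answers for one event | SAP 7 | Reaction under SAP 6.1 |
|---|---|---|
| (a) One form received, its field blank, the other fields blank | All blank: imputed related | Counted |
| (b) Two forms received, both blank | All blank: imputed related | Counted |
| (c) One form related, another blank | Not missing | Counted on any ordinary reading |
| (d) Earlier form not related, form in use at onset blank | Not missing: no imputation | Not counted |
| (e) Only form received is blank, a form never given is marked not related | Not missing: no imputation | Not counted |
| (f) 'Unknown' recorded, no form related | Not blank, not addressed | Not counted if read literally; no text says so expressly |

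Whether (e) and (f) can occur depends on the case report form, whose causality options are not in the documents. Case (d) needs only a patient with two forms and one empty field.

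**Step 2. Consistency.** In (a), (b) and (d) there is no judgement on the form in use. The first two are counted and the third is not. In (f) the physician has looked and not excluded a relationship, and the event is omitted although (a) is included.

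**Step 3. The cleaning rule.** Applied to a wholly blank causality item whose cleaning is not complete, it gives 'unknown'. The earlier sentence of SAP 7 gives 'related'. Both cannot apply.

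**Step 4. Direction.** Take as reference a count in which absence of a judgement on the form in use means related, which is the logic of the all-blank rule. Cases (d), (e) and (f) can only take events out of that count.

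**Step 5. Scale, by assumption.** The documents give no rate of partly blank or 'unknown' answers. The one design figure at hand is in Protocol 7.5.2: with n = 200 and hepatic toxicity incidence p = 0.20, at least 31 cases with probability about 95%.

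- Plan's figure: P(X ≥ 31) for X ~ Bin(200, 0.20) = 0.957. It reproduces. The expected number is 200 × 0.20 = 40.
- With a share m of affected patients lost, p = 0.20 × (1 − m) and the expected number is 200p.

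| m (assumed) | All 200 affected: expected, P(≥ 31) | Only the 100 children affected: expected, P(≥ 31) |
|---|---|---|
| 2% | 39.2, 0.943 | not run |
| 5% | 38.0, 0.915 | 39.0, 0.939 |
| 10% | 36.0, 0.845 | 38.0, 0.915 |
| 20% | 32.0, 0.606 | 36.0, 0.845 |

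The right-hand column adds Bin(100, 0.20) for adults to Bin(100, 0.20 × (1 − m)) for children, with expected number 20 + 20 × (1 − m). Here m is a share of patients, not of events: a patient leaves the count only if every qualifying event is affected. The 20% is the plan's figure for hepatic toxicity, not for all reactions.

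**The case against.** The wording has a good purpose. With three fields per event, an injection-only patient has empty tablet and dry syrup fields by design, and a rule that imputed on any blank would turn every such event into a reaction. This stands, and the fix must keep it. It also stands that single-form and fully blank patients are already counted, so the gap needs a specific combination of answers, and that residual blanks can be queried under Protocol 7.6.3.2.

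On 'unknown', the SAP is silent. Protocol 9.3 sets a reporting duty and Protocol 7.3.7 a follow-up duty; neither defines an analysis category. Exclusion is inferred from SAP 6.1, without sight of the form's response options. That is correct, and it is why the point is put as a literal reading. The silence itself still needs resolving.

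On the cleaning rule, a specific sentence would normally prevail over a general one. That is a reasonable guess at intent, but the SAP does not say so.

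Affected events do not disappear: SAP 8.2.3.2 tabulates all-causality events, and SAP 8.2.3 puts every reported event in listings. This limits the harm but does not restore the reaction splits.

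Finally, a remedy that counts an event as a reaction whenever any earlier form is blank would override a physician's 'not related' for the form in use. This is a sound warning, and the fix below avoids it in the main count.

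**Conclusion.** The point holds as a defect in a stated derivation rule: SAP 7 gives inconsistent results in identifiable cases, and the treatment of 'unknown' and of the cleaning rule is unresolved. It should be corrected before the final analysis, but it is of moderate weight. The analyses are exploratory by SAP 4.1, the events stay visible elsewhere, and the combination required may be uncommon.

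The size cannot be computed. The figures in the working show only what an assumed loss of 2% to 20% would do to one design quantity. They are not estimates.

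A reader might infer two stronger things. The first is that reactions will be undercounted overall. The documents do not show this: the all-blank imputation itself pushes the count up, no rates are given, and the net error against the truth is unknown. What can be said is that, relative to the SAP's own all-blank rule, the gaps remove reactions and never add them. The second is that the loss falls mainly on children. The dosing text makes use of two forms plausible in children on oral treatment, and Protocol 6.1 names safety of paediatric use as its only important missing information. But adults may also change form, no switching rates are given, and the 'unknown' gap has nothing to do with switching.

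**What to change.** In SAP 6.1 and 7:

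- Derive causality per event from the dosage forms received on or before onset, using the drug use record of Protocol 7.3.2. Ignore fields for forms never given.
- Count the event as a reaction if any such form is marked related, or if the form in use at onset is blank or 'unknown'. For events in the 28-day follow-up of SAP 8.2.3, define the form in use as the last one given.
- State how a blank, and likewise an 'unknown', for an earlier form is handled when the form in use is marked not related. Give a sensitivity count that treats it as related.
- Exempt causality from the cleaning rule for missing items.
- Tabulate how many reactions entered by a blank and how many by 'unknown'.

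Separately, Protocol 9.3 attaches the 24-hour duty to 'unknown' causality without limiting it to serious events, while the Protocol 9.1 table shows 'None' for non-serious events. These passages must be reconciled.

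The cost is a few sentences in the SAP, a clarification in the protocol and some programming. Form and administration period are already collected, so no new data are needed. The downside is that the reported reaction proportion may rise slightly; the tabulation by route of entry lets readers see by how much.
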